NCT Number: NCT04627727
Official Title: Effect of a Low FODMAP Diet on SIBO Breath Test Positivity
Document Type: Study Protocol and SAP
Document Date: 05/31/2024

PART B STUDY DESCRIPTION

Title of Protocol	Effect of a low FODMAP diet on SIBO
Principal Investigator	[name], MPH

B1. PURPOSE OF PROTOCOL

The primary objectives of this study are to evaluate the following in patients with SIBO:

1. The effect of LFD on bloating
2. The effect of LFD on hydrogen and methane levels in patients with bloating

B2. SIGNIFICANCE AND BACKGROUND FOR THE STUDY

Bloating is the most common symptom associated with disorders of brain-gut interaction (i.e., functional bowel disorders) such as irritable bowel syndrome, a disorder characterized by abdominal pain and altered bowel habits which affects up to 11% of world population. A common cause of bloating is small intestinal bacterial overgrowth (SIBO), a condition defined by excessive and/or abnormal type of bacteria in the small bowel. The potential role of SIBO for irritable bowel syndrome (IBS) was initially proposed by Pimentel et al. Using lactulose breath tests (LBTs), 78% of patients with IBS were also diagnosed with SIBO. After antibiotic therapy, 48% of patients no longer met the Rome criteria for IBS. A recent systematic review and meta-analysis concluded that the prevalence of SIBO is increased in IBS.

Dietary factors are known triggers of IBS related symptoms up to 65% of IBS patients report symptoms attributed to food. In double-blind, randomized, placebo-controlled trials; fructose and fructans have been shown to induce IBS symptoms in a dose-dependent manner.⁵ In fact, a diet low in fermentable, oligosaccharides, disaccharides, monosaccharides, and polyols (FODMAPs) is the most extensively investigated dietary intervention in IBS. A recent meta-analysis of seven randomized controlled trials comparing a low FODMAP diet (LFD) with various control interventions in 397 participants suggested a 31% greater likelihood in improvement of global IBS symptoms. In patients with diarrhea predominant IBS (IBS-D), Eswaran et al showed that those randomized to LFD had greater reductions in daily scores of abdominal pain, bloating, stool frequency, stool consistency, and urgency than the modified National Institute for Health and Care Excellence (NICE) diet. Others have also shown objective improvement in stool consistency of IBS-D patients with LFD using King's stool chart.

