Despite the clinical efficacy of LFD in improving symptoms of IBS-D, its mechanism of action is not clear. Recently, Zhou et al have shown FODMAPs induce colonic tight junction dysfunction and visceral hypersensitivity in rat models, both of which are reversible when rats were fed an LFD. They further showed that this effect of FODMAPs is mediated by microbial dysbiosis and elevated fecal lipopolysaccharide level. However, studies evaluating the effect of LFD on colonic permeability of humans are lacking. Studies have shown significant differences in intra-individual luminal and mucosal microbiome of patients with functional gastrointestinal disorders as well as an increase in *Prevotella* abundance in IBS patients with SIBO as compared with IBS patients without SIBO. Thus, the exact effect of FODMAP on intestinal permeability and mucosal microbiome in humans is not clear and needs further evaluation.

Several studies have also shown increase in the number of mast cells in the colonic mucosa of IBS patients. Although diet is perceived as an important trigger for mucosal mast cell increase and activation reported in IBS-D, it has been poorly investigated. The above reported study by Zhou et al also reported increase in colonic mast cell in rats fed on high FODMAP diet.

B3. DESCRIPTION OF RESEARCH PROTOCOL

A. Study Design – Overview, Methods, Procedures

Study Design

Consenting patients fulfilling the inclusion and exclusion criteria will undergo a 7-day screening period to assess baseline symptoms and then go on a 3-week low FODMAP diet. The total study duration will be approximately 5 weeks with visits at screening and Day 21.

Screening Visit

- Informed consent will be obtained from the subjects.
- Medical history including IBS and SIBO history will be obtained from the subjects
- Blood samples will be obtained
- Glucose SIBO breath test
- Daily questionnaires. Subjects will be instructed on the online daily questionnaires (described below) to be completed for the duration of the study.
- Subjects will be given two stool collection kits for at-home collection. One stool sample will be collected prior to beginning the treatment period. One stool sample will be collected on Day 21.

Visit 2 (Start of Diet/Day 0)

- Subjects will start the low FODMAP diet. Subjects will be told to ingest only Epicured provided items (excluding water) and to avoid eating anything outside of Epicured provided items.
- Baseline stool sample will be returned

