Final Visit (Day 21)

- Blood samples will be obtained
- Post-treatment stool sample will be returned
- Glucose SIBO breath test

Low FODMAP diet

Subjects who consent to participate in the study will have low FODMAP meals delivered to their home by Epicured. Epicured is a meal delivery service that provides ready-to-eat low FODMAP meals. Subjects will be required to provide their home address, name, phone number, and email address to Epicured. Epicured will provide meals and snacks to subjects for the duration of the 3-week low FODMAP period. Subjects will be told to only ingest Epicured provided items (excluding water).

Serological tests for intestinal permeability

The following serological markers for intestinal permeability will be assessed: serum lipopolysaccharide (LPS) activity measured with the Limulus Amebocyte Lysate assay (LAL, Hycult Biotechnology, the Netherlands) and serum zonulin levels (Catalog number 30-ZONSHU-E01; ALPCO, Salem, NH). This will be performed in our GI lab at BIDMC.

Serological tests for mast cell activation

Mast cell activation will be measured by tryptase level with the American Research Products assay (ARP, Waltham, MA)

Stool tests

Stool will be collected for 16S rRNA microbiome sequencing.

Concomitant Medications

Subjects will be allowed and advised to continue with their current IBS treatments (excluding rifaximin) as long as it was at a stable dose for 30 days prior to randomization.

Clinical variables

Data will be collected and stored via Research Electronic Data Capture (REDCap). Patients will be automatically emailed a link daily (via REDCap) with a REDCap link to the questionnaires listed below. Patients do not need access to WiFi, but do need Internet access (can be wired). If subjects do not have access to the Internet, they will not be eligible for participation.

- Rome IV Functional Bloating
Patients will be asked to complete a modified version of the Rome IV bloating questionnaire specific to the past 24 hours.
- IBS-SSS
Patients will be asked to record IBS-SSS and most common stool consistency of the day (measured using Bristol stool form scale).
- Diet compliance: Patients will also be asked to record their day's food and drink intake and record whether they were compliant with the FODMAP diet.

In addition, the following questionnaires will be administered at the end of the baseline period as well as the end of the 3-week LFD.

- Patient Reported Outcomes Measurement Information System (PROMIS)

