The Patient Reported Outcomes Measurement Information System (PROMIS) is a National Institutes of Health (NIH) set of tools used to provide information on patient outcomes in a variety of fields.
- Gastrointestinal PROMIS scales: PROMIS scales of belly pain, constipation and diarrhea will be administered to assess the severity of belly pain and diarrhea in our patients. PROMIS Belly pain questionnaire and PROMIS diarrhea questionnaire have five and six questions, respectively, which assess symptom severity on a 5 point Likert scale. Higher T-scores on these questionnaires refer to more severe gastrointestinal symptoms.
 - PROMIS belly pain asks how often did you have belly pain, severity of belly pain, interference with activities, bothersomeness and discomfort.
 - PROMIS diarrhea asks how many days did you have loose stools, interference with activities, bothersomeness, and how often you experience urgency.
 - PROMIS constipation asks how often did you experience hard stools, straining and incomplete evacuation.

Blood Collection

Any blood that is remaining after the analysis is completed will be stored frozen indefinitely at BIMDC for use in future studies. The sample will remain de-identified, but be labeled with the unique subject code. Information related to the subject's diagnosis, treatment, and study results will be retained and possibly used in future analysis and more information becomes identified regarding functional bowel disorders. PHI related to the stored samples will not be used in the future analysis and will be kept on BIDMC's secure server. Any samples that may be shared with collaborators will contain the subject code, but will not have any identifiable information or PHI.

B. Statistical Considerations

Sample Size Justification:

This study aims to recruit 30 subjects until 20 subjects are enrolled.

Data Analysis:

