All continuous variables will be tested for normality using the Shapiro-Wilk test. Normally distributed continuous data will be presented as mean (\pm SD) and will be compared pre-and post-dietary interventions using paired Student's t-test. Continuous data which are not normally distributed will be presented as median (range) and compared using Wilcoxon signed-rank test. Proportions will be expressed as percentages and compared using chi-square test or fisher exact test as appropriate. Since we anticipate that most of our tests will involve continuous data that is normally distributed, we based our power analysis on pre-post comparisons using paired t-tests. Assuming two-tailed tests, with alpha set at 5%, a sample size of 20 will provide 80% power to detect a medium effect size (i.e., Cohen's $d=.5$) when the pre-post correlation is $r=.7$.

C. Subject Selection

Patients with functional bloating diagnosed per Rome IV questionnaire and without any alarm features (rectal bleeding, weight loss, nocturnal symptoms, family history of inflammatory bowel disease or celiac disease) will be considered for the study if they had:

- i) Aged 18-65 years at the time of screening

Exclusion criteria

- i) individuals already on a LFD or other dietary restriction such as gluten free diet within the past 6 months
- ii) individuals with peanut, soy, or seafood allergies or insulin-dependent diabetes
- iii) known history of celiac disease, inflammatory bowel disease or microscopic colitis
- iv) prior small bowel or colonic surgery or cholecystectomy
- v) pregnant patients
- vi) antibiotics, excluding topical, in the past 3 months

B4. POSSIBLE BENEFITS

Subjects may experience improvement in their bloating symptoms.

B5. POSSIBLE RISKS AND ANALYSIS OF RISK/BENEFIT RATIO

Blood Drawing

The risks and discomforts of blood drawing from a vein include the possibility of pain or bruising at the site of the blood draw; occasional feeling of lightheadedness; and rarely, infection at the site of the blood draw.

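### Must the plan name a bloating endpoint and a diary window before the paired test for objective 1 can stand?

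*Combined protocol and SAP*

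**What the plan says.** - Section B1 lists "The effect of LFD on bloating" as the first of two primary objectives and attaches no endpoint to it.
- Section B3.A, Study Design: patients "will undergo a 7-day screening period to assess baseline symptoms and then go on a 3-week low FODMAP diet".
- Section B3.A, Screening Visit: "Subjects will be instructed on the online daily questionnaires (described below) to be completed for the duration of the study". This gives about 7 records before the diet and 21 on it for each patient.
- Section B3.A, Clinical variables: "Patients will be asked to complete a modified version of the Rome IV bloating questionnaire specific to the past 24 hours". No items or scoring are given. IBS-SSS is also recorded daily, and its role in objective 1 is not stated.
- The same section gives PROMIS fixed times: "the following questionnaires will be administered at the end of the baseline period as well as the end of the 3-week LFD". However, "PROMIS scales of belly pain, constipation and diarrhea will be administered", so none of the listed scales measures bloating.
- Section B3.B, Data Analysis: normally distributed data "will be compared pre-and post-dietary interventions using paired" t-tests, and other continuous data go to the Wilcoxon signed-rank test. Proportions go to chi-square or Fisher tests.
- The power statement is general: "Since we anticipate that most of our tests will involve continuous data that is normally distributed, we based our power analysis on pre-post comparisons", with n = 20, d = 0.5, r = 0.7 and two-sided alpha of 5%.

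**The concern.** A paired test needs one value before and one after for each patient. The bloating diary produces about 28 records, and the plan does not say how they reduce to two. A 7-day baseline is named, but not whether its mean or its last day is used. For the post value, the last diet day or the last diet week would fit the text and, read loosely, so would all 21 days. PROMIS cannot stand in, because it has no bloating scale.

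Two things would be at stake. If the summary were picked after seeing which gave the best result, the nominal 5% test on a primary objective would exceed 5%. Power also depends on the summary, because a single day is noisier than a weekly mean, and the stated d and r are tied to no particular score.

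**Working it through.** **1. The plan's own power figure.** Inputs from Data Analysis: n = 20, d = 0.5, r = 0.7, two-sided 5%.

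- Standardised paired difference: d / sqrt(2(1 - r)) = 0.5 / sqrt(0.6) = 0.645.
- Exact power from the noncentral t with 19 degrees of freedom: 78.2%. The normal approximation gives 82.3%, and n = 21 reaches 80%.
- The stated 80% is therefore sound on its own inputs. At other values of r, n = 20 gives 49.1% (0.4), 56.5% (0.5), 66.0% (0.6) and 91.8% (0.8).

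**2. What the text settles and what it leaves open.**

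- Pre value: the 7-day period exists to assess baseline symptoms, so a summary of the whole period is the natural reading. A last-day baseline would discard most of it.
- Post value: a comparison of before with after the intervention points to the end of the diet. Blood, stool, breath test and PROMIS are all taken there. An average starting on the first diet day is the least natural reading. What remains open is how much of the end of the diet to use.
- Instrument: the modified Rome IV form is the only one specific to bloating, although IBS-SSS is not formally excluded. A yes/no version could be analysed as a proportion of days, or could fall under the chi-square or Fisher clause.

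**3. Type I error if the window is chosen by its result.** All model inputs are assumptions. Daily score = patient + patient-by-period + day noise. Period variance is 1, with true period correlation 0.7 or 0.8. Noise variance is s2 = (1 - rel)/rel, with single-day reliability (rel) 0.4, 0.5 or 0.7. Day-to-day autocorrelation is 0, 0.3 or 0.5. That makes 2 x 3 x 3 = 18 cases, each with n = 20, 7 baseline days and 21 diet days.

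| Smallest paired-t p-value over | Type I error across cases |
|---|---|
| Week 3 only, against 7-day mean | 4.7-5.3% |
| Week 3 or all 21 days, against 7-day mean | 5.9-7.8% |
| Week 3 or last day, against 7-day mean | 7.4-8.6% |
| Week 3, last day or all 21 days, against 7-day mean | 8.5-10.5% |
| Those three, with last-day baseline also allowed | 12.5-16.3% |

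The first row is the important one: with one fixed window the level is 5%. The higher rows need selection on the p-value, and the last also needs a baseline reading that sits badly with the stated 7-day period.

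**4. Power by window.** Same model, with an assumed change of half a single-day SD, Delta = 0.5 x sqrt(1 + s2). Example with reliability 0.4 (s2 = 1.5), period correlation 0.7 and no autocorrelation, so Delta = 0.5 x sqrt(2.5) = 0.791:

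- One day against one day: variance of the difference 0.6 + 3 = 3.6; 0.791 / 1.897 = 0.417; power 42.4%.
- 7-day mean against 7-day mean: 0.6 + 3/7 = 1.029; 0.791 / 1.014 = 0.780; power 91.1%.

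Across the 18 cases, power is 42.4-61.9% for one day against one day, 54.5-76.7% for the 7-day mean against the last day, 74.4-95.7% against the week-3 mean, and 81.2-98.1% against all 21 days.

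With a constant effect, week 3 gives up 1.6-9.9 points to the 21-day mean. With a gradual onset the order reverses. If the effect builds linearly to its full size at Day 14, the 21-day mean carries 0.690 of it, and under the plan's d and r its power is 47%, against 78% for the last week.

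**The case for a change.** The strongest case for a change is that this is the first primary objective. The authors fixed the timing of PROMIS but not of bloating. A second daily instrument, IBS-SSS, leaves even the choice of score open. A reader of the eventual report could not confirm from this document that the window was set in advance, and a few sentences would settle it. The choice can also move power by tens of points. In the model above the pre-post correlation of weekly means runs from 0.46 to 0.75 and reaches 0.7 in only 4 of 18 cases, so the stated power is not established for bloating.

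The omission stands, as does the remark that the power figure is generic. The step from there to a needed change does not:

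- Nothing the plan states is wrong. The inflation comes from selecting on results, which the documents neither propose nor show.
- The large power contrast is with a one-day-against-one-day analysis that nobody has proposed. A daily diary with a 7-day baseline leads an analyst to averages.
- A restated power table would correct no error and would not alter the target of 20 patients.
- Days 15-21 with a minimum number of completed days is one reasonable preference among several. Any other single window protects the level equally well, and a completeness rule removes patients from a sample of 20.
- How to word a conclusion without a control group is a separate matter that does not depend on the diary window.

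**Conclusion.** No change to the plan follows. It leaves out a detail that a competent analyst fills in the ordinary course of the work, by taking the one bloating-specific score and comparing an end-of-diet summary with the 7-day baseline using the planned paired test. Done that way the test holds its 5% level, and under the assumed noise a weekly-mean comparison has about 74-96% power for a change of half a single-day SD.

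If the window were instead picked by its p-value, the error rate would be about 6-8% between averaged windows and about 7-10% with the last diet day also in play. The 12.5-16.3% range should carry little weight, because it needs a last-day baseline against the stated purpose of the 7-day period. All these sizes rest on assumed reliability, correlation and autocorrelation. That one fixed window keeps the 5% level does not depend on those values.

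### The only tests named for proportions assume independent groups, but the evident comparison is before versus after in the same patients

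*Combined protocol and SAP*

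**What the plan says.** B3.B, Data Analysis, gives a single rule for binary data: "Proportions will be expressed as percentages and compared using chi-square test or fisher exact test as appropriate". It does not say which proportions are meant, and no paired method for binary data appears anywhere in the document.

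The same paragraph does respect pairing for continuous data. Normally distributed variables "will be compared pre-and post-dietary interventions using paired Student's t-test", non-normal ones get the Wilcoxon signed-rank test, and the power statement assumes a pre-post correlation of 0.7.

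The design (B3.A) has one group. Patients "will undergo a 7-day screening period to assess baseline symptoms and then go on a 3-week low FODMAP diet". The item "Glucose SIBO breath test" is listed at the screening visit and again at Day 21. No second arm or between-group contrast is defined; randomization is mentioned once, in the concomitant medication rule, with no arms attached. The official title is "Effect of a Low FODMAP Diet on SIBO Breath Test Positivity". B1 says "The primary objectives of this study are to evaluate the following in patients with SIBO" and lists bloating and hydrogen and methane levels.

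**The concern.** Positive or negative at two visits in the same person is paired binary data. Chi-square and Fisher tests see only the two visit totals and assume that they come from different people. They discard what a before-after study collects: how many patients changed, and in which direction. The words "as appropriate" do not help, since they only choose between two independent-groups tests.

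The resulting p-value is not calibrated for a within-patient change. With positive correlation between visits it is usually too large, so the cost is lost power rather than false positives. With 20 patients there is little power to spare.

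**Working it through.** **The plan's own figure.** The only computed figure is 80% power for a paired t-test with n = 20, d = 0.5 and r = 0.7. The standardised paired effect is 0.5/√(2 × (1 − 0.7)) = 0.645. Two-sided at 5%, this gives 78.2% by the noncentral t (df = 19) and 82.3% by the normal approximation, so the figure is reproduced to a fair approximation. It concerns continuous data and does not bear on proportions.

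**Inputs for proportions.** From the documents: n = 20, two-sided alpha 5%, two visits, one group. Assumed, because the documents give neither: the positivity rates and the within-patient correlation phi.

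**Why the independent test misfires.** The variance of the paired difference in proportions is [p1(1−p1) + p2(1−p2) − 2·cov]/n, with cov = phi·√(p1(1−p1)p2(1−p2)). The independent-groups tests omit the covariance. At 60% on both visits and phi = 0.3, the true variance is 2 × 0.24 × (1 − 0.3)/20 = 0.0168. Without the covariance it is 2 × 0.24/20 = 0.024.

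**Example that needs no assumed phi.** Positivity falls from 12/20 to 6/20.

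| Became negative / became positive | Fisher | Chi-square | Mid-p McNemar | Exact McNemar |
|---|---|---|---|---|
| 6 / 0 | 0.111 | 0.057 | 0.016 | 0.031 |
| 7 / 1 | 0.111 | 0.057 | 0.039 | 0.070 |
| 8 / 2 | 0.111 | 0.057 | 0.065 | 0.109 |
| 12 / 6 | 0.111 | 0.057 | 0.167 | 0.238 |

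Mid-p McNemar, with m discordant pairs and k the smaller count, is 2·P(X ≤ k) − P(X = k) for X ~ Binomial(m, ½). For 6 v 0 this is 2/64 − 1/64 = 0.016.

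**Exact enumeration of every paired 2×2 table, n = 20.** Cell probabilities come from the two rates and phi; chi-square is uncorrected. Entries are rejection rates (%) at phi 0 / 0.3 / 0.5.

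| Scenario | Fisher | Chi-square | Exact McNemar | Mid-p McNemar |
|---|---|---|---|---|
| No change, 60% | 2.4 / 0.7 / 0.2 | 4.8 / 1.9 / 0.6 | 2.2 / 1.6 / 0.8 | 4.1 / 3.5 / 2.4 |
| 60% to 30% | 35 / 32 / 29 | 46 / 46 / 44 | 34 / 45 / 56 | 44 / 58 / 73 |
| 40% to 15% | 32 / 28 / 25 | 44 / 42 / 40 | 28 / 34 / 38 | 38 / 48 / 58 |
| 80% to 50% | 41 / 38 / 36 | 53 / 53 / 52 | 37 / 48 / 58 | 47 / 61 / 76 |

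Phi 0.5 is at or near the largest value possible for the three change scenarios (maxima 0.53, 0.51 and 0.50), so the phi 0.3 figures are the fairer illustration. Using Fisher only when an expected count is below 5 gives nearly the chi-square figures at 60%.

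**All patients positive at baseline.** Phi is then undefined and the table above does not apply.

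| Fall | Fisher | Chi-square | Mid-p McNemar |
|---|---|---|---|
| 20/20 to 14/20 | 0.020 | 0.008 | 0.016 |
| 20/20 to 15/20 | 0.047 | 0.017 | 0.031 |
| 20/20 to 16/20 | 0.106 | 0.035 | 0.063 |

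Here uncorrected chi-square gives smaller p-values than the paired test, so the planned tests are not reliably conservative.

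**The case against.** **The comparison is inferred.** The sentence on proportions does not mention pre and post, positivity is in the title but not in the B1 objectives, and no cut-off for a positive test is given. Chi-square or Fisher would suit a contrast of separate groups, such as baseline-positive versus baseline-negative patients. This is fair, but no such contrast is stated either, and the patient's own baseline is the only comparator that the design provides. The missing endpoint definition is a further gap; it does not make the named tests suitable.

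**The harm is mainly lost power, and much of the gain comes from mid-p.** This stands. At phi 0.3, exact McNemar is no more powerful than chi-square in any of the three scenarios, and at phi 0 mid-p is slightly less powerful than chi-square. The case for pairing does not rest on power alone: the planned p-value is the same for 6 v 0 as for 12 v 6.

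**If all patients are positive at baseline, little changes.** With the usual small-count rule Fisher would be chosen, and at 14, 15 or 16 of 20 still positive it falls on the same side of 5% as mid-p McNemar. This also stands, but the listed eligibility criteria do not require a positive breath test, so the case cannot be presumed. In that case the conversion proportion with its interval is the better summary.

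**It is minor.** The plan expects mostly continuous data, and those tests are paired. That limits the weight of the point, but an analyst who followed the text would still run the wrong test on the outcome in the title.

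**Conclusion.** The concern holds: as written, the plan assigns paired binary data to tests for independent groups. That pre-post positivity is the intended comparison is inferred from the one-group design, the two breath tests and the title.

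At phi 0.3 with no change at 60%, Fisher rejects 0.7% and chi-square 1.9% of the time against a nominal 5%. Chi-square gives up 6 to 12 percentage points of power to mid-p McNemar in the three scenarios (42 v 48, 53 v 61, 46 v 58). These sizes depend on assumed rates and phi; the 12/20 to 6/20 example does not depend on phi. The point should be fixed, but its reach is limited: the B1 objectives are mainly continuous with paired tests, and the power statement is untouched.

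**What to change.** Replace the sentence on proportions with: *Pre-post proportions will be compared with the mid-p McNemar test, reporting the discordant counts and the paired difference in proportions with a 95% CI.* Fix this one version before the data are analysed, since exact and mid-p can fall on opposite sides of 5% (7 v 1: 0.070 and 0.039).

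Because B1 speaks of patients with SIBO while eligibility does not require a positive test, add: *If all analysed patients are breath-test positive at baseline, the proportion converting to negative will be reported with an exact binomial 95% CI.* For example, 5/20 = 25%, Clopper-Pearson 95% CI 9% to 49%.

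The plan should also say that positivity is the proportion meant and how a positive test is defined. If a comparison between separate groups is intended, it should be named, and chi-square or Fisher kept for that alone.

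The cost is a few sentences and no new data. The statistical downsides are small: mid-p does not strictly guarantee 5% (worst case at n = 20 is 5.04%, at a discordance rate of 0.82, on a grid from 0.01 to 1), and it has slightly less power than chi-square if the two results are uncorrelated.

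### Breath-test positivity would be compared before and after the diet with chi-square or Fisher's exact test, which ignore that the same patients are tested twice

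*Combined protocol and SAP*

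**What the plan says.** The design in section B3.A has a single arm. Consenting patients "will undergo a 7-day screening period to assess baseline symptoms and then go on a 3-week low FODMAP diet". The list of procedures for the screening visit and the list for Day 21 both contain "Glucose SIBO breath test", so each patient contributes a before and an after result.

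The cover page gives the official title as "Effect of a Low FODMAP Diet on SIBO Breath Test Positivity", which is a yes/no outcome. Section B1, under primary objectives, lists "The effect of LFD on hydrogen and methane levels in patients with bloating", which is continuous. The title field of Part B does not mention positivity.

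In section B3.B, Data Analysis, continuous variables are compared before and after the diet by paired t-test, or by Wilcoxon signed-rank test if not normal. For proportions the only rule is "Proportions will be expressed as percentages and compared using chi-square test or fisher exact test as appropriate". On sample size the same paragraph says "we based our power analysis on pre-post comparisons using paired t-tests", and claims 80% power for n=20, d=0.5, r=0.7, two-sided 5%. The plan gives no positivity cut-off, no expected positive or conversion rate, no power for a proportion and no paired test for a proportion.

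**The concern.** Chi-square and Fisher's exact test compare two separate sets of patients. Here the two sets are the same 20 people. What bears on a diet effect is how many patients turn from positive to negative and how many turn the other way. The planned tests see only the two totals. The plan respects pairing for continuous data and drops it for proportions, and with no comparison group the natural use of the proportions rule is before against after.

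At stake is the p-value attached to the outcome in the official title. It could miss a consistent one-way change, or give the same answer to a consistent change and to an inconsistent one.

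**Working it through.** **1. The plan's own figure.** Inputs from Data Analysis: n=20, d=0.5, r=0.7, two-sided alpha 5%. The standardised mean change is dz = d/√(2(1−r)) = 0.5/√0.6 = 0.645. The noncentrality is 0.645 × √20 = 2.887 on 19 degrees of freedom. Power from the noncentral t is 78.2%; the normal approximation gives 82.3%. The stated 80% is reproduced to within rounding. It covers any continuous pre-post outcome, bloating scores as well as gas levels, but not a proportion.

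**2. What the planned test cannot see.** Illustrative counts: 12/20 positive at screening, 6/20 at Day 21. Exact McNemar is the two-sided binomial test on the patients who changed.

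| Patients who changed | Fisher | Chi-square | Exact McNemar |
|---|---|---|---|
| 6 turn negative, 0 positive | 0.111 | 0.057 | 2 × 0.5^6 = 0.031 |
| 10 turn negative, 4 positive | 0.111 | 0.057 | 2 × P(X≤4; 14, 0.5) = 0.18 |

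The planned p-values are identical in both rows. The paired p-values differ almost sixfold.

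**3. Size under a threshold model (assumption).** The documents give no cut-off or positive rate. Assume one normally distributed level with r=0.7 that falls by 0.5 SD, and a fixed cut-off that makes 30-80% positive at screening. Take "as appropriate" to mean chi-square, with Fisher when an expected count is below 5. Enumerating the four pair cells exactly at n=20 gives power (%):

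| Positive at screening | 30% | 40% | 50% | 60% | 70% | 80% |
|---|---|---|---|---|---|---|
| Planned rule | 10.3 | 14.8 | 15.5 | 14.9 | 15.5 | 13.6 |
| Exact McNemar | 8.5 | 14.0 | 17.6 | 19.0 | 17.4 | 12.3 |
| Mid-p McNemar | 17.7 | 24.8 | 29.1 | 30.6 | 28.9 | 22.7 |

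Mid-p gains between 17.7 − 10.3 = 7.4 and 30.6 − 14.9 = 15.7 points. With no effect, the planned rule rejects in 0.5-0.7% and mid-p in 1.3-2.6%. Both stay below 5%, and the planned rule is the more conservative.

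**4. A stronger effect (assumption).** Let 60% positive fall to 30% with no patient turning positive. Mid-p McNemar reaches p<0.05 from 5 changes against 0, so its power is P(Binomial(20, 0.3) ≥ 5) = 76%. The planned rule has 44%, exact McNemar 58%. The loss against mid-p is 32 points.

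**5. The corner where the direction turns.** Section B1 says "The primary objectives of this study are to evaluate the following in patients with SIBO", but Subject Selection does not require a positive breath test. Suppose all 20 are positive at screening and 5 turn negative (20/20 to 15/20). Fisher gives 0.047 and exact McNemar 2 × 0.5^5 = 0.0625, so the planned test is the more liberal of the two. Mid-p gives 0.031. With 4 turning negative, Fisher gives 0.106 and mid-p 0.0625, so at n=20 the planned rule and mid-p both first cross 5% at 5 conversions.

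Neither is a fair test there, because a group selected as positive can only improve. If 20% would retest negative without any diet effect (assumption), P(Binomial(20, 0.2) ≥ 5) = 37% of trials would be significant; at 10% the figure is 4%.

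**The case against.** The best defence is that the plan treats proportions as a minority case. B1 already names gas levels as the breath-test part of the primary objectives, the Part B title omits positivity, and the rule for proportions does not itself say pre-post. That stands, and it limits the point: the main breath-test analysis is paired and is covered by the power statement. It does not rescue the rule for proportions. The plan names no independent groups to compare, and positivity is in the official title. Chi-square could be read loosely as McNemar's chi-square, but the text does not say so, and naming Fisher beside it points to the independent-groups pair.

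A second defence also partly stands: the power gain depends on choosing mid-p. Exact McNemar is 1-2 points below the planned rule at 30%, 40% and 80% positive, and only 2-4 points above it at 50-70%.

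Stronger readings that a reader might infer, and why they are not supported:

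- *Levels and positivity would give opposite verdicts.* Under the model in step 3, simulated with 40,000 trials per setting, the number positive also fell in 94-98% of the trials in which levels were significant. The usual disagreement is significant against not significant, and it comes mainly from dichotomising. It occurs in about 63-68% of trials with the planned rule and still in about 49-62% with mid-p McNemar.
- *Twenty patients cannot suffice for positivity.* If 40% of all patients turn negative and none turn positive, exact McNemar has 87% power. The plan simply states no such rate.
- *The wrong test can only cost power.* Step 5 shows otherwise when all are positive at screening.
- *There is a multiplicity error across the two gases and bloating.* That is a separate question, and it would rest on a success rule that the documents do not contain.

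**Conclusion.** The point holds as a correctable error of analysis choice. If the plan is followed as written, positivity gets an independent-groups test on paired data.

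The worked example in step 2 depends on no model and is enough to establish this. The size of the loss does depend on assumptions: about 7-16 points of power against mid-p McNemar with 30-80% positive at screening and the plan's d and r dichotomised, and 32 points at 60% falling to 30% with no reversals. The direction depends on who is enrolled, and the documents leave that open: conservative at 30-80% positive, possibly more liberal than exact McNemar if nearly all are positive.

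The mismatch between the official title and B1 is a matter of labelling. A reader might infer that no breath-test endpoint was chosen, but B1 lists gas levels among the primary objectives. What is missing is a statement of where positivity ranks and how it is defined.

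**What to change.** 1. For pre-post proportions, replace the sentence in Data Analysis with: *Proportions at screening and Day 21 will be compared with McNemar's test (mid-p), with the paired difference, its 95% CI and the 2x2 table of both visits.* Keep chi-square and Fisher for independent subgroups only. Name mid-p explicitly, since the exact version gains little or nothing here.
2. State whether a positive screening breath test is in practice an entry condition, reconciling B1 with Subject Selection. If it is, report the share still positive at Day 21 with an exact confidence interval and make no pre-post test.
3. State that the gas levels of objective 2 are the primary breath-test outcome and that positivity, with its cut-off, is secondary. Align the official title with this.
4. Add that the stated power (78.2% by exact calculation) applies to continuous pre-post outcomes only.

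The cost is a few sentences and a title alignment. Both breath tests are already scheduled, so there are no new visits, samples or patients, and power for continuous outcomes is unchanged. Making positivity primary would be different: under the model in step 3, 80% power with mid-p McNemar needs 55-72 patients, so the sample size would have to be redone for a paired proportion.
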